An Audio Music Self-management to Improve ART Adherence in Rural Georgia
IRB#00055077

An Audio Music Self-management to Improve ART Adherence in Rural Georgia

Protocol Dated 03/04/2016

NCT01786148

An Audio Music Self-management to Improve ART Adherence in Rural Georgia

Protocol

[name], [name], [name], [name], [name]

Sponsor: National Institute of Nursing Research/National Institute of Health

July 14, 2012

Updated October 21, 2013

Updated February 8, 2015

Updated August 11, 2015

Updated February 11, 2016

Updated March 4, 2016

Background

a. Specific Aims:

The project has three primary aims and two exploratory aims.

1.0 Revise and adapt the Live Network (LN) program and manual for rural persons living with HIV/AIDS (PLWHA) and develop into a mobile application.

2.0 Conduct a randomized controlled trial to test the efficacy of the program. When compared with an educational music control condition at 3, 6, and 9 months post-baseline, those randomized to the LN will have:

H1: Significantly higher mean antiretroviral therapy (ART) adherence rates (measured by pill counts, self report).

H2: Significantly higher mean levels of ART drug levels in hair sample analyses.

H3: Significantly better clinical indicators: higher mean CD4 lymphocyte counts and percents, a larger proportion achieving virologic suppression (proportion with HIV RNA PCR <50 copies/ml), and smaller proportion with evidence of drug resistance, all as measured by medical record review.

3.0 Explore: a) the effects of LN on symptoms and symptom management; b) the roles of self-efficacy, outcome expectancies, and personal goal setting as mediators, and depression and health literacy as moderators of adherence

4.0 Evaluate the acceptance and adoption of the LN and educational program (EP) mobile application software (app) by examining: a) the antecedent influences of performance expectancy, effort expectancy and hedonic motivation on the behavioral intent-to-use and usage (frequency and duration) of the LN and EP mobile apps; and b) the moderating effects of electronic health (eHealth) literacy and smartphone experience on behavioral intent and subsequent LN/EP mobile app usage.

H1: Performance expectancy, effort expectancy, and hedonic motivation have direct, positive associations with behavioral intent to use the LN/EP mobile apps.

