RCT: Inclusion criteria for the study are: 1) HIV infection; 2) initiating ART for the first time (except women who may have had ART during pregnancy) or changing ART regimen within the past 3 months due to side effects or virologic resistance; or 3) HIV+ individuals with a detectable viral load \geq 40copies/ml; 4) HIV+ individuals on ART medication 5) \geq 18 years of age; 6) English speaking; and 7) willing to complete 4 assessments, monthly unannounced pill counts, and collection of hair samples, be randomly assigned to either condition, and participate in study activities that include using smart phone and mobile app. Persons will be excluded from the study if they are not HIV infected, homeless, are a minor under 18 years of age and therefore unable to give independent informed consent, are unable to read or understand English since all of the questionnaires and the audio program and manual will be in English, have a history of or self-report bilateral hearing loss, cognitive impairment (inability to comprehend the informed consent document), are actively psychotic, severely depressed/suicidal, or pose a risk of harm to themselves or others (Brief Symptom Inventory; BSI), since these persons may not be capable of using the mobile app or completing the assessments. Depending on the severity, these persons will be walked to or referred to the mental health counselor, once the mental health issues have been addressed, they may be re-screened for eligibility. Substance users will not be excluded from the study, except if they display the above mentioned mental health characteristics or pose a risk of harm to themselves or others.

b. Setting

The study sites are within 5 health district sites that provide care to HIV+ persons in rural counties in Georgia outside the 20-county Metropolitan Atlanta Statistical area (MSA). The sites of the project are:

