RCT: Sources of information will include baseline, 3, 6, and 9- month follow-up assessments and tracking of usage of mobile app conducted solely for the purpose of this research. Assessments will include assessments of adherence to antiretroviral medications and, measures of symptoms, depression, self-efficacy, attitudes, goals, demographic information including substance use, and health literacy. Physiologic measures will include ART drug levels in a small hair sample (100 strands) cut from the occiput (back of head) at each time point. Lab results for CD4, viral load, and drug resistance will be extracted from medical records consistent with the study time points. Study assessments will be conducted in person using ACASI coincident with provider appointments. They will last about 3 hours. Monthly unannounced pill counts will be conducted via smart phone using the camera and pill count survey within app with assistance from the clinical research coordinator as needed. As part of our reliability testing, up to 60 participants will be asked to repeat their pill count about 24 hours after baseline. Hair samples will be collected in person by study personnel on-site at each time point. Tracking usage of the app will be done via the mobile web application which will send messages to the HIPAA compliant server each time a participant uses the app. Participants will be assigned to one of two conditions: an educational music program (EP) or the LN treatment condition. All participants will receive the usual care at their respective HIV care agencies. Evaluation information will be obtained about the satisfaction and use of the programs at the end of the RCT study. The option of 3, 6, and 9 month follow up study assessments administered via phone call will be offered to participants who are unable to complete in person visits. If this option is elected the hair sample and visual analog scale data will not be collected.

d.1.b Other interactions

Participants will receive reminder calls and text messages regarding study appointments. Text messages will also remind them to listen to the LN & EP.

d.2 Respondent burden

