The target sample size is 200 participants with 100 allocated to each group. Taking into account projected attrition of about 40 persons, we expect a final sample size of 240. Given our approach using multi-level longitudinal models (MLM) for these 200 subjects, 2 groups at 4 time points, we are 95% confident that power levels between 84% to 98% will achieve minimal detectable differences of 0.4 (within time and group by time) and 0.5 (between groups) (small-to-moderate effect sizes) for random effects subjects variance equal to 1. Covariate adjustments should further reduce variability and detectable effect sizes while increasing power. Additionally, to address the differences in proportion achieving virologic suppression and drug resistance, a chi-square test for a sample size of 200 yields a small-to moderate effect size (ω) of 0.1981 for 1 degree of freedom (2 x 2 table) at 80% power and 5% level of significance.

h.2 Plans for data management and analysis

h.2.a Data management Procedures for data management and monitoring will be initiated during the start-up phase. The project coordinator will coordinate the organization and processing of forms, and schedule and implement checks of data quality and completeness. Data from the ACASI files will be saved in the QDS data warehouse. Data will be backed up on a regular basis to prevent loss of data. Data will be transferred electronically from the sites to a secure password protected, HIPAA-compliant server at Emory University. A data-checking plan based on each questionnaire will be used to look for suspicious entries. Data monitoring will include scheduled checks for completeness every 2-4 weeks. Data sets from all assessment points will be merged as necessary to answer the research questions. Personal goals will be reported by the participant and typed into the database for qualitative analysis. They will be analyzed for the dimensions of content, specificity, effectiveness, and control. [name] will oversee the final quality assurance/quality control data reviews. She will design and conduct the statistical analyses; assist as with designing research forms and data entry; and collaborate with the

investigators on analysis and interpretation. We have successfully used these procedures with the pilot project and other research projects.

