Satisfaction (Aim 1) Two assessments will be conducted and analyzed to determine participant satisfaction with the mobile app in general, LN program and interactive manual. Both times, we will ask questions about likeability, usage rates, ease of use, acceptability, satisfaction, relevance, favorite song, understandability, and suggestions for improvement. The first assessment will entail observations and discussions with rural PLWHA while using the mobile app in focus group format. Observations and discussions will be recorded and content analyzed for themes, which will inform final revisions to the LN app. The second feasibility analysis will be the Program Evaluation Survey at the end of the study. Scaled responses to questions related to the above criteria will be analyzed using descriptive statistics and written comments will be entered into nVivo software and content analyzed for themes. We will also describe and evaluate the usage data from the web application designed to track app usage. We will determine average usage patterns and compare between groups (LN vs. EP).

Outcomes (Aim 2) All covariates will be evaluated to determine if any differences exist at baseline between the 2 groups (LN and EP), as well as testing for interactions (moderation) between groups and time. Inter-correlation among the covariates will also be evaluated. Multicollinearity diagnostics (variance inflation factors, tolerance, condition index) will be used to determine which covariates should remain in the subsequent models. MLM longitudinal models as detailed above will be used for each outcome (H1: adherence, H2: drug levels, and H3: CD4, viral load, drug resistance) to test differences between the 2 groups (group main effect), test for changes/differences from baseline to 3, 6 and 9 month (time main effect) and test for group by time effects (i.e. changes from baseline that are differences between the 2 groups) adjusting for significant covariates/moderators as needed. Appropriate link functions (e.g. logit, Poisson, other) will be assessed for each outcome within the MLM.

Exploratory outcome, mediators and moderators (Aim 3) Symptoms and symptom management scores will be examined using MLM as described above. Self-efficacy, outcome expectancy and personal goals are mediators in our model and meet the criteria for mediators as defined by Baron and Kenny⁴⁴

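### The 84–98% power in h.1 does not apply to a 0.5 follow-up difference if it is tested by a group main effect that averages in baseline

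*Combined protocol and SAP*

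**What the plan says.** Specific Aim 2.0 frames the efficacy hypotheses as follow-up comparisons: "When compared with an educational music control condition at 3, 6, and 9 months post-baseline, those randomized to the LN will have" better adherence, drug levels and clinical indicators. Participants must be willing to "be randomly assigned to either condition" (a.2, RCT criteria). Under d.2.1, "Sources of information will include baseline, 3, 6, and 9- month follow-up assessments", so the first of the four visits precedes treatment.

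On size, h.1 says: "The target sample size is 200 participants with 100 allocated to each group". Enrolment is 240, to allow for about 40 lost. The power statement is made "for these 200 subjects, 2 groups at 4 time points" and reads "power levels between 84% to 98% will achieve minimal detectable differences of 0.4 (within time and group by time) and 0.5 (between groups", "for random effects subjects variance equal to 1". No residual variance or within-subject correlation is given, and h.1 does not define what the between-group 0.5 measures.

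In h.2.b, Outcomes (Aim 2), a longitudinal multilevel model is used for each outcome "to test differences between the 2 groups (group main effect), test for changes/differences from baseline to 3, 6 and 9 month (time main effect", together with a group-by-time test, described as a between-group difference in change from baseline. The section does not say which of these tests decides H1–H3, and it does not name the baseline value of the outcome as a covariate.

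**The concern.** In a model with baseline as one of four time levels, an averaged group main effect is the LN–EP difference in four-visit means. Randomisation makes the expected baseline difference zero, so a quarter of the average carries no treatment effect. The follow-up difference that Aim 2 asks about enters the test at three quarters of its size.

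If the 0.5 in h.1 is taken as the difference at 3, 6 and 9 months, the stated power does not belong to this test. If it is the four-visit average, h.1 is describing a larger follow-up effect than its wording suggests. At stake are the meaning of the power statement and the use of a weak test for the main comparison when the data already planned support a stronger one.

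**Working it through.** **Inputs.** From h.1: 100 per arm, four time points, subject variance 1, differences 0.4 and 0.5, power 84–98%. From h.2.b: 5% level. Assumed here: two-sided tests, random-intercept model, complete data, equal visit weights, no covariates, and residual variance r, which the plan does not give and which is therefore varied. Except for the 3-df test, power = Φ(Δ/SE − 1.96).

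**1. The plan's own figure.** For a four-visit average, SE = √[2(1 + r/4)/100]. With Δ = 0.5 and r = 0.5, SE = √(2 × 1.125/100) = 0.150 and Δ/SE = 3.33, giving 91.5%. Other values are 94.2% (r = 0), 88.5% (r = 1) and 84.0% (r = 1.73). At r = 0.5 the other claims also fit: group by time at 0.4 gives 83.8% (3 df), and within time at 0.4 in one arm gives 0.4/√(2 × 0.5/100) = 4.0, or 97.9%. The stated range therefore reproduces if 0.5 is the four-visit average.

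**2. A follow-up difference of 0.5 under the same test.** The arm differences are (0, 0.5, 0.5, 0.5), with mean 1.5/4 = 0.375.

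- r = 0: 0.375/0.1414 = 2.652, power 75.5%
- r = 0.5: 0.375/0.150 = 2.50, power 70.5%
- r = 1: 0.375/0.1581 = 2.372, power 66.0%
- r = 1.73: power 60.1%

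Reaching 84% needs 1 + r/4 ≤ 50 × (0.375/2.954)² = 0.806, which is impossible with subject variance 1. Conversely, a four-visit average of 0.5 means 0.5/0.75 = 0.67 at follow-up.

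**3. The planned group-by-time test, same 0.5 at follow-up.**

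- 3 df: noncentrality 50 × Σ(dⱼ − d̄)²/r = 50 × 0.1875/r = 9.375/r, referred to F on 3 and 594 df.
- 1 df (follow-up mean minus baseline): SE = √[2(4r/3)/100]. At r = 0.5, 0.5/0.1155 = 4.33.

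**4. Follow-up mean adjusted for baseline.** SE = √[2(1 + r/3 − 1/(1 + r))/100]. At r = 0.5 this is √(2 × 0.5/100) = 0.10 and 0.5/0.10 = 5.0. At r = 1 it is √(2 × 0.8333/100) = 0.1291 and 0.5/0.1291 = 3.87.

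| Power for 0.5 at all three follow-ups | r = 0.5 | r = 1 | r = 1.73 |
|---|---|---|---|
| Four-visit group main effect | 70.5% | 66.0% | 60.1% |
| Group by time, 3 df | 96.5% | 72.8% | 47.1% |
| Group by time, 1 df | 99.1% | 86.5% | 64.4% |
| Follow-up mean, baseline-adjusted | 99.9% | 97.2% | 89.5% |

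**5. Which r fits h.1.** At a difference of 0.4, group by time has 52% (3 df) or 69% (1 df) power at r = 1, and 31% or 46% at r = 1.73. The group-by-time claim in h.1 therefore needs r of about 0.5 or less (3 df), or 0.69 or less (1 df).

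**The case against.** The strongest reply is that no stated figure is wrong. The 84–98% reproduces on the four-visit reading, and the plan also has, and powers at 0.4, a group-by-time test that baseline does not dilute. Both points stand. They rule out the stronger conclusion a reader might draw, that the trial has at most 75.5% power or would miss a real 0.5 benefit one time in four. At r = 0, where 75.5% arises, group-by-time power approaches 100%; at r = 0.5 it is 96.5% or 99.1%.

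A reader might also set 66.0% against 97.2%, or 60.1% against 89.5%, as the gain from the repair. Those rows use residual variances at which the group-by-time claim in h.1 fails, and they compare with the main effect alone. At r = 0.5 the gain over the 1-df group-by-time test is only 99.1% to 99.9%.

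The ceiling is conditional. Section h.1 expects covariates to reduce variance, without saying by how much. To reach 84% they would have to remove 19% of subject variance at r = 0, 32% at r = 0.5 (0.806 − 0.125 = 0.681) or 44% at r = 1. If the 1 were total variance, with an assumed intraclass correlation of 0.5, power at 0.375 would be 91.8%; but h.1 assigns the 1 to the subject effect. Under reference coding with an interaction, the group coefficient is not a four-visit mean at all, and h.2.b does not state the coding.

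Scope is limited too. Virologic suppression and drug resistance are powered separately by chi-square, and a model of all the monthly pill counts would not carry the 0.75 factor.

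What the reply leaves untouched is that h.2.b lists a group main effect as a test of the arms, does not say which test decides, and h.1 omits the residual variance on which group-by-time power depends.

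**Conclusion.** The point holds for one test. If the group main effect is the average over all four visits, a 0.5 difference at every follow-up is tested as 0.375, with power of at most 75.5% and 70.5% at the residual variance that best matches h.1. The 84–98% does not apply to a 0.5 follow-up difference tested this way. It does apply to a four-visit average of 0.5, which is 0.67 at follow-up, and h.1 does not say which it means.

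This rests on 100 per arm, subject variance 1, equal visit weights, complete data, no covariate adjustment, zero expected difference at baseline and a constant difference afterwards. Retaining all 240 would raise the ceiling to 82.8% (0.375/√(2/120) = 2.905), still below 84%. It does not show that the trial is underpowered. It shows that the power statement and the Aim 2 hypothesis are not tied to the same contrast, and that the main effect is a poor choice for that hypothesis.

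**What to change.** In h.2.b, Outcomes (Aim 2), for the continuous outcomes, replace the four-visit group main effect as the test of the arms with the LN–EP contrast over 3, 6 and 9 months from the same multilevel model. Enter the baseline value as a covariate, or constrain the arm means to be equal at baseline. State that this contrast is the test of the continuous parts of H1–H3. It has more power than either planned test at each positive residual variance tabulated.

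In h.1, restate power for that contrast and give the assumed residual variance or within-subject correlation. If the present figure is kept, state that 0.5 is a four-visit average corresponding to 0.67 at follow-up.

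The cost is a text change in two sections, made before outcomes are compared by arm. Baseline is already collected; no participants, visits or measures are added. The chi-square calculation for the binary outcomes is unaffected.

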We conducted a pilot RCT at the same site to compare the program with usual care (at least 2 visits with a Nurse Educator). We enrolled 77 persons who started or changed ART within the previous 6 months. Participants were randomized 2:1 to LN (n = 51) or standard care (n = 26) and completed baseline (T1), 6 week (T2), and 12 week (T3) assessments and monthly pill counts (PC). Blood draws measured plasma antiretroviral medication trough levels at 12 weeks, an innovative measure of adherence. Significance for this small sample pilot was set at $p \leq .1$. Mean age was 44.7 yrs; 65% were male; 88% were African American; participants were HIV-infected for 9.6 years (median). Median monthly income was \$674. At T3 we found adherence declined over time for both groups; however the drop was greater for the control group compared to the LN group: 67% (14 of 21) of controls but only 52% (22 of 42) of intervention subjects dropped below baseline values (NS). While not statistically significant, PCs at T3 were higher for intervention participants (77.8% vs. 70.6%). Also at T3, 80.5% of LN subjects vs. 72.7% of controls had antiretroviral plasma trough levels at or above therapeutic range (n=63, NS). CD4 and viral load (VL) were analyzed using multilevel mixed models. There was a larger proportion of LN group with undetectable VL log (≤ 1.88) at all time points. VL log (inverse transformed) yielded a significant group by time interaction ($t=1.890$, $p=0.067$, and model deviance change $\chi^2=3.07$, $df=1$, $p=0.08$) for the LN. No significant differences were seen for CD4. Adherence self-efficacy scores improved in the LN group from T1 to T3 ($\chi^2=5.1$, $df=2$, $p=0.080$). No significant changes were seen for the control group ($\chi^2=2.6$ ($df=2$), $p=0.273$). Wilcoxon pairwise post hoc tests using Bonferroni corrected alpha=0.033 indicated significant differences between T1 and T3 ($Z=-2.39$, $p=0.017$) and between T2 and T3 ($Z=-2.39$, $p=0.017$). Self-efficacy had the largest effect sizes seen in this study; the largest changes occurred between T1 and T3 indicating that the study should be run longer to establish sustainable improvements. For the LN group, ART self-efficacy scores increased by 6.05 ($sd=12.97$) for an estimated effect size of 0.47, a medium effect size. Participants with higher CES-D scores (depressive symptoms) at T1 were 1.08 times more likely ($p=0.03$) to have drug trough levels below the therapeutic range at T3. There were no differences between or within groups in numbers of symptoms or symptom distress. Small sample size and short duration of follow-up limit our results. All

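### The 80% power quoted for virologic suppression and drug resistance belongs to a single-visit 2x2 comparison, not to the longitudinal tests planned for these outcomes

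*Combined protocol and SAP*

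**What the plan says.** Hypothesis H3 under Aim 2 (Specific Aims) predicts, at 3, 6 and 9 months, a larger proportion with HIV RNA below 50 copies/ml and a smaller proportion with drug resistance in the LN arm than in the EP arm.

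Section h.1 sets the numbers: "The target sample size is 200 participants with 100 allocated to each group", after "projected attrition of about 40 persons". One sentence gives power of 84% to 98% for the multilevel models, for differences of 0.4 and 0.5. A separate sentence covers the two H3 proportions: "a chi-square test for a sample size of 200 yields a small-to moderate effect size" "of 0.1981 for 1 degree of freedom", at 80% power and the 5% level. It names no visit, no proportions, no baseline share and no within-person correlation.

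Section h.2.b, Outcomes (Aim 2), assigns every outcome to longitudinal multilevel models, listing viral load and drug resistance under H3. The planned tests are a group main effect, a time main effect running from baseline to 3, 6 and 9 months, and a "test for group by time effects (i.e. changes from baseline that are differences between the 2 groups"). On the outcome scale it says only that "Appropriate link functions (e.g. logit, Poisson, other) will be assessed for each outcome within the MLM". It mentions no chi-square for H3 and does not say which model term decides the hypothesis.

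**The concern.** A power figure is useful only if it refers to the test that will be reported. Here the sizing test is cross-sectional with 1 degree of freedom, and the analysis is longitudinal with baseline among the responses. That matters in two ways.

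- Group by time compares changes from baseline. On the logit scale, a change from baseline carries the sampling error of the baseline cells, which is large when few people are suppressed at entry. With four visits the term also has 3 degrees of freedom.
- A group main effect averaged over all four visits includes a visit at which randomised arms should not differ, so the effect is diluted.

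The entry criteria make a low baseline share possible: they include first-time ART starters, people switching for resistance and "HIV+ individuals with a detectable viral load" of at least 40 copies/ml. If the interaction were taken as the H3 result, a real suppression benefit of the planned size could be reported as no virologic effect. With the deciding term unnamed, it could also be chosen after the results are seen.

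**Working it through.** **1. The plan's own figure.** Noncentrality = N x w^2 = 200 x 0.1981^2 = 7.85. With 1 df at the 5% level this gives 80.0% power. Equivalently, (1.960 + 0.842)/sqrt(200) = 0.1981. The figure reproduces for one 2x2 table of 200 people.

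**2. Inputs for the planned tests.** From section h.1: 100 per arm, four visits, w = 0.1981, 5% level. Assumed, because the documents give no values:
- logit link, no missing visits, and the same w at 3, 6 and 9 months;
- mean follow-up suppression 60-80%;
- 5-70% suppressed at baseline, equal in both arms;
- random-intercept SD 1 to 3 on the logit scale.

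**3. Formulas.** Each cell's log-odds has variance 1/[n p(1-p)]. Its covariance with another visit in the same arm is Cov(Y1,Y2)/[n p1(1-p1) p2(1-p2)], with Cov(Y1,Y2) obtained by integrating over the random intercept. Power of a 1-df contrast is approximately Phi(effect/SE - 1.96). The 3-df test uses the corresponding quadratic form and a noncentral chi-square.

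**4. One setting in full.** Mean follow-up suppression is 70%, so w = 0.1981 means 60.9% vs 79.1%, a log odds ratio of 0.886. SD is 1.8. The figures below sum the two arms.
- *9-month difference.* Variance 0.0420 + 0.0604 = 0.1024, SE 0.320, ratio 2.77, power 79%.
- *Change from baseline to 9 months, 10% suppressed at entry.* The baseline cells add 2 x 0.1111 = 0.2222, and the baseline-to-follow-up covariance is 0.0250. Variance 0.1024 + 0.2222 - 2 x 0.0250 = 0.2746, SE 0.524, ratio 1.69, power 39%.
- *The same change, 50% suppressed at entry.* The baseline cells add 0.0800 and the covariance is 0.0288. Variance 0.1248, SE 0.353, ratio 2.51, power 71%.
- *Group effect averaged equally over four visits, 10% at entry.* The effect shrinks to 0.75 x 0.886 = 0.664. The follow-up covariance is 0.0335. Variance (0.2222 + 3 x 0.1024 + 6 x 0.0250 + 6 x 0.0335)/16 = 0.0550, SE 0.235, ratio 2.83, power 81%.
- *Average over 3, 6 and 9 months.* Variance (3 x 0.1024 + 6 x 0.0335)/9 = 0.0565, SE 0.238, ratio 3.73, power 96%.

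**5. Across the assumed range (closed form).**

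| Suppressed at baseline | Group by time, 3 df | 9-month change from baseline |
|---|---|---|
| 5% | 16-22% | 22-30% |
| 10% | 27-38% | 34-46% |
| 20% | 44-59% | 48-62% |
| 30% | 54-71% | 55-72% |
| 50% | 62-85% | 59-82% |
| 70% | 55-88% | 55-82% |

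Over the same settings the four-visit average has 63-96%, the 9-month contrast about 79%, and the 3/6/9-month average 92-99%. In this grid, group-by-time power of about 80% appears only at 50% or 70% baseline suppression. In all but one such setting it also needs SD 3, a within-person correlation of about 0.54.

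**6. Simulation check.** Random-intercept logistic models were fitted by maximum likelihood with 61% vs 79% suppressed, SD 1.8 and 400 trials per setting (Monte Carlo error about 2 points). At 5, 10, 20, 30 and 50% baseline suppression, the 3-df test had 27, 39, 56, 64 and 75% power and the 9-month change 31, 42, 62, 63 and 72%. A 9-month chi-square had 79-86%. A group term fitted without an interaction had 84-94%.

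**The case against.** The strongest reply is that group by time is only one of the planned tests. The group main effect is listed first, and H3 is worded as a between-group difference at 3, 6 and 9 months, not as a change from baseline. A group term without interaction had 84-94% power in the simulations above, and 72-98% in a second set with a sustained effect and random-intercept variance 1 to 9. This stands: nothing in the documents says that the interaction decides H3. It does not rescue the stated 80%, which is not the power of that term either. If the effect builds up linearly to 9 months, the group term falls to 39-71% in the second set.

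A reader might take the simulated 27-75% as the power of this trial. The documents do not support that. The range depends on the baseline share, the correlation, the trajectory and the link, none of which they fix; logit is only an example. The one variance given in h.1 is 1, with no scale stated. With correlation 0.5 and baseline suppression close to follow-up suppression, group-by-time power is about 80-83%, and higher correlation takes it further up.

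A reader might also infer that a real benefit would be missed more often than not. In the simulation that holds only at 5-10% baseline suppression, and low baseline suppression is not established. The entry criteria also admit people switching for side effects and people on ART, and section c.4 allows expansion to everyone on ART.

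The pilot may look like a precedent, since its viral-load result "yielded a significant group by time interaction". That was inverse-transformed log viral load, with a 1-df deviance change. The proportion undetectable was described separately, with no interaction test.

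Finally, the chi-square sentence in h.1 could be read as an implied plan to run that test. Section h.2.b sends each outcome to the multilevel model, and even on this reading the visit is unnamed.

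**Conclusion.** The mismatch holds. The 80% at w = 0.1981 is correct for an unadjusted LN-EP difference at one visit and does not describe the tests in h.2.b. For suppression, under the assumptions listed in the working, group-by-time power is about 16-62% when at most 20% are suppressed at entry. It reaches about 80% or more only with roughly half or more suppressed at entry and, in most settings, strong within-person correlation. A group effect averaged equally over the four visits has about 63-96%, because the baseline visit dilutes it.

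These ranges are conditional on inputs that the documents do not give. No power was computed for drug resistance; for that outcome only the mismatch between sizing and analysis is shown. The change should be made, but the documents do not show that the trial is underpowered on H3.

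**What to change.** In h.1, state that w = 0.1981 at 80% power applies to an unadjusted LN-EP difference in proportions at one follow-up visit. Print any group-by-time power only with its assumed baseline share, within-person correlation and effect trajectory.

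In h.2.b, Outcomes (Aim 2), for the two H3 proportions, make the deciding test the LN-EP difference over the post-baseline visits. This can be either the 9-month contrast (about 79% unadjusted for suppression) or the 3/6/9-month average (about 92-99% if the effect is sustained). Enter the baseline value as a covariate, not as a response row, and report group by time as supportive. The 80% would match a covariate-adjusted model only approximately, since the power of that model was not computed.

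The cost is wording in two sections, with no new data or participants. The downside is that a less favourable power figure would be printed for group by time, and that term would no longer decide the H3 proportions.
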